## ABBREVIATIONS USED

AAE	anticipated adverse event
ACTG	AIDS Clinical Trials Group
AE	adverse event
AFB	acid-fast bacilli
AHF	Alliance Healthcare Foundation
ALT	alanine transaminase
ANC	absolute neutrophil count
AST	aspartate transaminase
AUDIT	Alcohol Use Disorders Identification Test
AVRC	Antiviral Research Center
BIT Core	UCSD Center for AIDS Research Bioinformatics and Information Technologies Core
BUN	blood urea nitrogen
CBC	complete blood count
CDC	Centers for Disease Control and Prevention
CMD	Core Medical Device
CMP	comprehensive panel
DAST-10	Drug Abuse Screening Test
DHFS	digital health feedback system
DOT	directly observed therapy
FDA	U.S. Food and Drug Administration
β-HCG	human chorionic gonadotropin
HLA	human leukocyte antigen
HHSA	County of San Diego Health and Human Services Agency
HIV	human immunodeficiency virus
IEM	ingestible event markers
IRB	institutional review board
IS-RM	ingestion sensor-enabled Rifamate
MDR-TB	multi-drug-resistant tuberculosis
NIH	National Institutes of Health
OCCAMS	Open Source Clinical Content Management System
OCHCA	County of Orange Health Care Agency Pulmonary Disease Services
PDA	positive detection accuracy
PDH	Proteus Digital Health
PHI	protected health information
PHQ-9	Patient Health Questionnaire-9
PHS	County of San Diego Public Health Services
PI	Principal Investigator
QD	once a day
SAE	serious adverse event
SAP	statistical analysis plan
SGOT	serum glutamic oxaloacetic transaminase
SGPT	serum glutamic pyruvic transaminase
SOC	standard of care
TB	Mycobacterium tuberculosis complex

UA	urinalysis
UADE	Unanticipated Adverse Device Effect
UCSD	University of California, San Diego
ULN	upper limit of normal
USP	United States Pharmacopeia
WHO	World Health Organization
WOT	wirelessly observed therapy

## SCHEMA

### AHF TB 001

#### **Wirelessly Observed Therapy in Comparison to Directly Observed Therapy for the Treatment of Tuberculosis**

A pilot feasibility trial characterizing use of a digital health feedback system (DHFS) using ingestion sensor-enabled fixed-dose combination of isoniazid-rifampin (Rifamate) and comparing this to directly observed therapy (DOT) for treatment of Mycobacterium tuberculosis complex (TB).

Design: AHF TB 001 is a multi-site, randomized, open-label, controlled interventional pilot feasibility study comparing the efficacy, characteristics of use, persistence and safety of a digital health feedback system (DHFS) (Proteus Digital Health, Inc., Redwood City, CA, USA) using ingestion sensor-enabled fixed-dose combination Rifamate (IS-RM) in comparison to directly observed therapy (DOT) using standard of care (SOC) with isoniazid plus rifampin, or Rifamate in TB-infected subjects. Subjects will be ineligible if they have any evidence of drug resistant TB or prior intolerance to study drug. Those who are found to be eligible will participate in a two-week investigation (Phase 1) of the positive detection accuracy and characteristics of use of the DHFS in the TB patient population. Eligible patients who elect to continue in Phase 2 will then be randomized 2:1 to monitoring intervention with the ingestion sensor-enabled Rifamate (IS-RM), or to DOT SOC. This study will be conducted at the UCSD AVRC, the San Diego County TB Clinic, and the County of Orange Health Care Agency Pulmonary Services Clinic.

[figure not shown]
Duration: Up to 12 months

Sample Size: 75-100 subjects in Phase 1; 50 intervention and 25 control SOC subjects in Phase 2

Study Population: Adult men and women being treated for TB with at least isoniazid and rifampin who are able to use the DHFS mobile device, and to tolerate a wearable sensor patch

Regimen: Subjects will be randomized 2:1 to TB treatment using DHFS ingestion sensor-enabled Rifamate (IS-RM) or SOC

**Figure 1. AHF TB 001 Study Schema**

## 1.0 HYPOTHESIS AND STUDY OBJECTIVES

### 1.1 Hypotheses

- 1.1.1 Direct confirmation of TB medication dosing by DHFS is feasible for monitoring TB treatment.
- 1.1.2 DHFS can be used as an alternative to SOC DOT for monitoring and documenting completion of TB treatment.
- 1.1.3 The cost of TB target treatment using DHFS is comparable or favorable when compared to DOT for monitoring a comparable number of targeted doses.
- 1.1.4 DHFS is safe for use in TB treatment.
- 1.1.5 Patient satisfaction with DHFS use for TB treatment is rated as ‘satisfactory’ or higher.
- 1.1.6 Healthcare worker and physician satisfaction with DHFS for TB treatment is rated as ‘satisfactory’ or higher.
- 1.1.7 DHFS subjects have similar or better self-efficacy scores than control subjects receiving SOC DOT during and at the end of the trial.

### 1.2 Study Objectives

#### Primary

- 1.2.1 Phase 1: Determine positive detection accuracy (PDA, direct confirmation of TB medication ingestion) of the DHFS when compared to a healthcare worker witnessing actual TB medication ingestion. PDA will be based upon proper DHFS use. PDA will be determined using an intention-to-treat and an adjusted analysis.
- 1.2.2 Phase 2: Determine the percentage of witnessed doses by DHFS and SOC, respectively. Witnessed doses by DHFS is defined as the total number of dose ingestions confirmed by DHFS, divided by the total number of prescribed witnessed dose ingestions for TB treatment. Witnessed doses by SOC is defined as the total number of dose ingestions that are actually witnessed by a healthcare worker, divided by the total number of prescribed witnessed dose ingestions for TB treatment.

#### Secondary

- 1.2.3 Determine the percentage of subjects completing > 80% prescribed witnessed dosing for TB treatment using DHFS and SOC, respectively.

- 1.2.4 Summarize the total number of lapses in witnessed doses and longest duration of witnessed treatment lapse during use of DHFS and SOC, respectively.
- 1.2.5 Model cost of treatment based upon data obtained during use of DHFS and SOC, respectively.
- 1.2.6 Characterize adverse events for DHFS and SOC using summary statistics.
- 1.2.7 Characterize subject responses to post-study questionnaires to collect information regarding their experience with the DHFS and the usability of the system, using summary statistics. Questionnaire responses by subjects will be examined by study reviewers from the AVRC to develop recommendations regarding the usability of the system.
- 1.2.8 Characterize provider responses to post-study questionnaires to collect information regarding their experience with the DHFS and the usability of the system, using summary statistics. Questionnaire responses by providers will be examined by study reviewers from the AVRC to develop recommendations regarding the usability of the system.
- 1.2.9 Characterize generalized scores on habitual self-control, self-efficacy beliefs, depression scale (PHQ-9), alcohol use (AUDIT), and drug use (DAST-10) questionnaires at the start and end of study within the intervention group, and between the intervention and control groups.
- 1.2.10 Define the characteristics of those subjects with < 80% adherence, including demographics, disease characteristics, and self-reported metrics by individual instruments, for example the PHQ-9.

## 2.0 INTRODUCTION

### 2.1 Background

**Eradication of disease due to *Mycobacterium tuberculosis complex* (TB) has been for decades a major policy goal of the Centers for Disease Control (CDC), the Global Alliance for TB Drug Development, and the World Health Organization (WHO).** Poor adherence to therapy has long been recognized as a barrier to effective treatment of TB infection. Inconsistent and interrupted treatment, in combination with HIV co-infection, has led to rising numbers of TB cases and the emergence of drug resistant TB. One third of the world's population (~2 billion people) are infected with latent TB, over 9 million people a year develop active TB, and mortality approaches 2 million deaths annually.

Treatment of active TB requires 6-12 months of combined therapy. Public health authorities in all countries recommend that TB treatment be administered by short course directly observed therapy (DOT), in which a healthcare worker observes medication ingestion events and provides written verification of treatment adherence and completion. While highly reliable when performed appropriately, DOT is resource intensive, time consuming, and represents the largest

single cost of TB treatment [1]. Although DOT is the WHO's recommended TB treatment standard, its implementation has been attenuated due to cost. Even in the U.S., DOT is not consistently applied; "modified DOT," or self-administered therapy, is more often used due to budget limitations. Some TB public health programs in the U.S. do not use DOT at all, or use DOT only for high-risk patients; in the private sector, self-administered therapy is the rule rather than the exception. Bi- and tri-weekly dosing is used to lower the cost of DOT, despite evidence that daily dosing of TB medication is more effective [2, 3]. In the absence of DOT, there is no method of reliably determining when and if patients actually ingest their medication.

Alternative methods for assessing adherence such as patient questionnaires, pill counts, patient diaries, and prescription refill rates have been shown to be inaccurate and to overestimate adherence [4-6]. For example, a review of prescription databases can show when refills occur, but does not show when dosing errors occurred, or most importantly, the date the patient stopped taking the drug [7-10]. Limitations also apply to measurements of drug concentrations in plasma, which do not take into account the fact that patients' drug taking behavior is a dynamic process that changes over time and is subject to strong bias, with white coat effects that typically increase adherence in the 24-48 hours before a scheduled visit to the clinic or laboratory [11-13]. The electronic bottle cap, such as the medication event monitoring system device, has also been used as a potential surrogate for drug dosing [14]. However, several limitations have been reported with this methodology, including mismatches between electronic cap opening and actual intake (more than one dose taken or no dose taken) and patients obviating electronic assessment by decanting pills from a bottle having an electronic cap to an alternative daily decanter or a weekly pill box [4-6].

Even fully implemented DOT has drawbacks for adherence. DOT by definition does not allow naturalistic observation of an individual patient's drug taking behaviors. One concept emphasized in medication adherence literature is the link between a patient's sense of self-efficacy, that is, an individual's perception of their ability to perform a specified behavior or set of behaviors [15], and their ability to execute satisfactory adherence. In one recent study comparing modified DOT with self-administered drugs, Gross et al. observed that DOT does not enable a patient to learn to manage their own drug taking behavior, a factor that may detract from improvements in medication compliance in the long term [16].

There is clearly an unmet need for an alternative to DOT that can reliably and efficiently confirm medication ingestion events and provide verification of TB treatment adherence and course completion. This tool should be accurate and easy for both the patient and healthcare worker to use, and ideally should provide feedback to the patient to guide their compliance with TB treatment.

## 2.2 Rationale

A digital health feedback system (DHFS) (Proteus Digital Health, Inc., Redwood City, CA, USA) has been developed to provide wirelessly observed therapy (WOT) as a reliable, efficient, scalable, and cost-effective alternative to DOT for sharing complete and accurate medication data in near real-time among patients, prescribing physicians, public health workers, pharmacists, and other healthcare providers. WOT represents a potential new paradigm for TB therapy monitoring, which can be utilized by public health workers and outreach workers to

confirm TB treatment. **The ultimate goal of this protocol is to utilize WOT as an alternative to DOT for daily real-time assessment of TB medication adherence in an ambulatory setting, providing individualized mobile healthcare using prompt, targeted feedback for the management of TB infected patients.** This pilot trial provides an opportunity to lead the way forward in the clinical practice of TB control with this innovative U.S.-developed technology. The results from this trial will demonstrate the feasibility and the utility of this technology to other countries that have a higher TB burden.

DHFS represents the first technology that allows date- and time-stamping of actual ingestions of oral medications, instead of surrogate measures of ingestion [17]. It can also provide specific information regarding the types and doses of multiple drugs taken simultaneously. DHFS allows secure medication-taking data to flow to patients, prescribing physicians, pharmacists, and other healthcare providers [17, 18]. The data shared between patients and healthcare providers affords the opportunity 1) to assess the regularity of medication-taking and 2) to support patient medication taking behavior in near real time to encourage optimal adherence.

DHFS consists of two main components: 1) an ingestion sensor, and 2) a wearable sensor to detect and record ingestion and physiological activity. The ingestion sensor is smaller than a sesame seed (1.0 mm x 1.0 mm x 0.45 mm) and composed of minerals and metals in the human food chain. The sensor can be encapsulated with prescribed medication. When ingested, the sensor utilizes gastric fluid and electrolytes to communicate information to an adhesive-backed wearable sensor. The wearable sensor is worn on the torso and confirms and records the identity, date, and time of sensor ingestion. The wearable sensor interprets each individual ingestion sensor's information as unique. The communication process lasts approximately 5-7 minutes and is unnoticed by, and not detectable beyond, the system user. Like an ingested sesame seed, the remainder of the ingestion sensor is then passed and excreted with the stool.

In this manner, DHFS is capable of directly confirming when, how much, and how many doses of prescribed medication have been ingested. The wearable sensor decodes and records the information from the ingestion sensor, and date- and time-stamps ingestions and physiological metrics such as rest and activity. All of the recorded data is sent wirelessly using encryption to a computing device (such as a mobile device or a personal computer) and is subsequently uploaded to a secure, centralized data storage location. The data can then be formatted and directed back in a similarly secure manner to the patient or those designated by the patient, so they can keep track of their own medication-taking and other activities of daily living [17-19].

The DHFS has been studied in healthy volunteers, as well as in patients with TB, heart failure, hypertension, diabetes, schizophrenia, and bipolar disorder as their primary disease. The ingestion sensor has been cleared via the 510(k) pathway and has received the CE mark in the EU. The following is an excerpt from the FDA-cleared device label which summarizes the technical performance: "A total of 412 study subjects have participated in Pill ingestion studies representing 20,993 ingestible sensor ingestions. In comparison with direct observation, the ingestible sensor was detected in 97.3% of ingestions, with correct identification in 100%." The latest configuration of the system, which includes wearable sensor version RP4 and the Miniature Ingestible Event Marker Tablet dose form, underwent post-approval, formative testing, in which sensitivity for ingestion sensor detection versus directly observed ingestion was 99.4% (95% CI 97.9-99.8%), and there were no false positive detections. Regarding ingestion

sensor safety, the following is also abstracted from the FDA-cleared device label: “nausea/vomiting occurred in 1%, constipation in 0.5%, asthma attack in 0.2%, abdominal cramping in 0.2%, non-cardiac chest pain in 0.2% and bitter taste in mouth in 0.2%. None of these adverse events were considered serious and all resolved spontaneously” (Ingestible Sensor Investigator’s Brochure, Rev 4).

Wearable sensor version RP2 and RP3 have been cleared via the 510(k) pathway and have received the CE mark in the EU. The following is an excerpt from the FDA-cleared device label, which summarizes the safety of these earlier wearable sensor versions: “A total of 492 study subjects have participated in clinical studies representing 6,407 days of Patch (wearable sensor) use with or without ingestible sensor ingestion. Sixty-two (12.6%) of these users experienced adverse events related or possibly related to the Patch. Sixty-one of these AE were self-limited skin rashes localized to the Patch placement site, and 1 was a self-limited episode of pain at the Patch location unassociated with skin rash. None of these adverse events were considered serious.” The latest wearable sensor version (RP4), which remains investigational at present, has undergone testing in 38 subjects. Four AE were reported (10.5% of subjects), all localized to the wearable sensor placement site and mild in severity. Three of these AE were erythematous rashes at the wearable sensor location; one of these rashes transiently manifested itself as non-erythematous skin discoloration (“secondary NESD”) on the path to full resolution. The fourth AE was an episode of “primary NESD” (i.e., there was no antecedent erythematous rash reported at the wearable sensor location). Primary and secondary NESD have been encountered with previous wearable sensor versions. The investigator hypothesized that per-protocol premature removal of the wearable sensor in these studies (typically after several hours, as opposed to intended 7-day wear) significantly contributed to the occurrence of these four RP4-related AE (Wearable Sensor Investigator’s Brochure, Rev 4).

A proof of feasibility study has been conducted in 30 TB patients and published from two clinical sites in the U.S., using an earlier prototype of the current WOT system. This was a prospective, non-randomized, single-blinded study to evaluate the feasibility and safety of an early version of the DHFS in patients with active TB and in the continuation phase of treatment. Study participants were monitored during 10 consecutive daily DOT visits where ingestible event markers (IEM) were ingested separately at the time of medication dosing. At each visit, participants ingested 2 tablets along with their TB medications. Of the 20 tablets ingested by each patient (over 10 visits), 18 had IEM attached and 2 placebo tablets contained no IEM. The IEM system showed high positive and negative detection accuracies in identifying medication ingestions [20]. The DHFS has been updated substantially since this early study.

This pilot trial project will utilize DHFS to assess medication adherence to ingestion sensor-enabled Rifamate (IS-RM) reliably, in an ambulatory setting in order to accurately characterize medication taking behavior of adult patients undergoing treatment for TB that includes at least INH and RIF. The system will provide a means of directly confirming medication adherence and identifying non-adherent patients to County healthcare workers, who can then provide prompt adherence intervention, thereby preventing treatment failure. The system can also provide individualized healthcare using prompt-targeted feedback tailored to individual TB patients.

The ingestible sensor will be over-encapsulated with a fixed-dose combination of isoniazid-rifampin (Rifamate), IS-RM; thus DHFS will capture actual ingestion of IS-RM. In this

feasibility study, subjects meeting eligibility criteria will initially have ingestion of IS-RM confirmed by DHFS for two weeks with simultaneous healthcare worker witness of actual IS-RM medication ingestion to evaluate the positive detection accuracy of DHFS. Alternatively, during Phase I, subjects may take Rifamate with co-ingestion of an encapsulated edible sensor. Subsequently, those eligible subjects who wish to continue will be randomized to either DHFS or SOC DOT. DHFS has previously been studied for up to 4 months in patients with chronic disease. Phase 2 of this trial will look at persistence of use from 4 weeks until completion of TB treatment (up to a maximum of 12 months on study).

Per CDC guidelines, DOT can take place five, three, or two times per week, with the medication dose adjusted to the frequency of medication taking. Although DOT is the gold standard for monitoring therapy, it can be difficult to execute perfectly, since subjects may miss DOT appointments for vacation, work, or other reasons, and conversely DOT workers may miss appointments due to overscheduling or transportation failure. Thus, the adherence metrics chosen for this study need to carefully take into account the unique nature of DOT, as adherence determined by the number of witnessed doses ingested. The optimal adherence metric for this study is the total number of actual witnessed dose ingestions divided by the total number of prescribed witnessed dose ingestions, captured by DOT or via DHFS. This parameter, the percentage of witnessed doses, will be reported for the duration of the study (per week, per month and over the entire study period). The percentage of witnessed doses in this trial captures effective monitoring of TB treatment via DOT and DHFS, and allows calculation of adherence with SOC DOT at varying intervals, e.g., five, three, or two times per week.

TB treatment has largely grown up through convention and analysis of treatment failures in traditional clinical practice, rather than extensive clinical trials with pharmacokinetic and therapeutic drug monitoring. Thus patterns of drug administration given via DOT five, three, or two times per week have been deemed acceptable based on treatment failure rates, with adherence  $\geq 80\%$  of prescribed dosing estimated by key opinion leaders as adequate for TB treatment [21]. Daily DOT may give more favorable pharmacokinetic profiles for isoniazid and rifampin with their relatively short half-lives (isoniazid-1.5 hours [fast acetylators] to 4 hours [slow acetylators]; rifampin-3 hours). Random and sparse sampling of therapeutic drug concentrations may confirm adherence monitoring data obtained via DHFS and SOC DOT; and pharmacokinetic evaluation of daily and five, three, and two times weekly dose administration may be analyzed. Stored plasma samples in this trial may allow future pharmacokinetic analysis with random sampled dosing history data providing the foundation for sound pharmacological interpretation of dose- or exposure-dependent variations in drug response in ambulatory care of TB.

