#### 6.2.1.5 Randomization

Subjects who wish to continue and remain eligible will be randomized 2:1 to DHFS IS-RM or to the control group receiving standard of care (SOC). Randomization for treatment assignment will be done centrally via the electronic database.

If the subject is randomized to the control arm, public health will provide isoniazid and rifampin, or Rifamate and DOT as per their routine. Please remind the subject to fill medication and contact public health as soon as possible. Please contact public health to inform them subject has been randomized to SOC DOT. The public health nurse assigned to this case should be handed the cost analysis data collection materials. The public health nurse will collect and perform quality control of the DOT forms used, but the outreach workers that actually perform the DOT.

If the subject is randomized to the intervention arm they will be given a 14-30-day supply of treatment medication, DHFS IS-RM, from the AVRC pharmacy on the entry day.

### 6.2.2 On-Study Evaluations, Phase 2

#### 6.2.2.1 Day 0

Subjects randomized to the intervention will undergo clinical assessment including toxicity. They will receive training and instruction will take place on home use of DHFS, continuous patch wearing, use of mobile device with application screen. They will be monitored for correct patch use. Pre-study interviews will collect subject attitudes to mobile devices

and internet usage, as well as their understanding of taking anti-mycobacterial medications thus far and what they would like to gain from use of the PDH monitoring system. Self-report questionnaires will be administered on a mobile device. The subject's plasma will be drawn and stored only if they are subjects seen at the AVRC. Cost data collected. The patient will be instructed to take IS-RM at the clinic. From this point on study personnel and public health workers will check adherence data provided by DHFS daily and perform adherence intervention as necessary.

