## 9.3 Randomization

Subjects will be randomized 2:1 to DHFS or SOC. Randomization will be done centrally via the study database.

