## 9.4 Sample Size and Accrual

Phase 1: For phase 1, both groups will use the DHFS for 2 weeks, and we will estimate the confidence interval around an estimate of the detection accuracy of the DHFS by taking the ratio of the sensor-enabled ingestion recorded events compared to the witnessed doses. Assuming that each of 75 subjects completes 2 weeks of DHFS dosing and has a total of three witnessed doses each week (a total of 450 dosing events) and that the overall rate of positive detection is 95%, then the 95% confidence interval around the point estimate of 95% accurate detection would be  $\pm 2.0\%$ . If the detection accuracy was 97%, then the 95% confidence interval around the point estimate of 97% accurate detection would be  $\pm 1.6\%$ .

Phase 2: The primary aim of phase 2 is to assess the percentage of prescribed witnessed doses completed over the entire study period for each subject and to compare the DHFS arm to the DOT arm. This metric captures the persistent efficacy of the DHFS ingestion sensor system and allows comparison to SOC DOT of varying intervals (5 times, 3 times, or 2 times per week that may occur in the SOC). Sample size calculations were based on a two-sided, two-sample t-test to compare the differences in adherence percentages by treatment arm using different mean/standard deviation scenarios. Calculations were performed using the R statistical package (version 2.14.0) ([www.r-project.org](http://www.r-project.org)).

In choosing a sample size for this pilot study, we considered issues of cost, feasibility, as well as how large an effect size would be of interest to spur further study of this intervention in this population. Assuming a two-sided alpha of 0.05, an adherence percentage in the DOT arm of 90%, and a common standard deviation of 6%, we will need 75 participants (50 DHFS arm and 25 DOT arm) to detect a 5% difference (i.e. 95% adherence percentage in DHFS arm) with 92% power.

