#### Phase 2 (Percentage of Witnessed Doses)

A mixed effects regression model will be used to determine if the WOT intervention arm will produce greater percentage of witnessed doses compared to the DOT standard of care arm at treatment end. This model will include time, treatment arm, and time-by-treatment arm interaction terms. In addition, any covariates, which are simultaneously unbalanced at baseline and associated with the outcome, will be included in the model. Time will be treated as a categorical variable. A significant treatment effect will be concluded if the p-value for the time-by-treatment interaction contrast in the model is  $\leq 0.05$ . Permutation tests may be implemented to verify that valid p-values will be obtained even if model assumptions are not correct. Note that the linear mixed model seamlessly accommodates different times of measurement as well as missed measurements and data from subjects who are lost to follow-up. Generalized estimating equation (GEE) models will be used as the sensitivity analysis method.

Note that when considering percentages of witnessed doses over the entire study period in aggregate, this model reduces to a multiple linear regression, and the independent variable of interest is the treatment arm.

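### Phase 2 does not prespecify county in the randomisation or the primary model, and plans no check on whether DOT workers shared by control subjects correlate their outcomes

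*Combined protocol and SAP*

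**What the plan says.** **Sites and delivery.** The Schema says the study is "conducted at the UCSD AVRC, the San Diego County TB Clinic, and the County of Orange Health Care Agency Pulmonary Services Clinic". Section 3.2 recruits from San Diego and Orange Counties, and nothing confines either county to one arm. Under section 3.5.2, County healthcare workers deliver control DOT. Section 6.2.1.5 refers to "the outreach workers that actually perform the DOT" and has the public health nurse collect and check the DOT forms.

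**Cause of missed doses.** Section 2.2 says subjects may miss DOT appointments and that "conversely DOT workers may miss appointments due to overscheduling or transportation failure". Under section 9.2.1 a control dose counts only if a healthcare worker witnessed it, so a missed worker visit lowers the primary endpoint directly.

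**Randomisation.** Section 9.3 gives a 2:1 ratio and says "Randomization will be done centrally via the study database". No stratification factor is named.

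**Analysis.** Of the Phase 2 mixed model, section 9.6.1 says: "This model will include time, treatment arm, and time-by-treatment arm interaction terms". Other covariates enter only if they are found to be both imbalanced at baseline and related to the outcome. For the whole-study percentage, the section says the model becomes a multiple linear regression on arm. GEE is the sensitivity method, with no cluster unit named.

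**Sample size.** Section 9.4: "Sample size calculations were based on a two-sided, two-sample t-test to compare the differences in adherence percentages by treatment arm". It takes "an adherence percentage in the DOT arm of 90" per cent, 95% in the DHFS arm, a common SD of 6%, and 50 v 25 subjects, for 92% power.

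**The concern.** Two separate issues are easily run together.

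**County.** Different public health agencies run DOT in the two counties, so the percentage of witnessed doses may well differ between them. If it does, a model without county leaves that variation in the residual, and an unstratified allocation lets the county mix drift between arms. The covariate rule in 9.6.1 is a weak safeguard. It makes the primary model depend on the observed data, and it omits county when county predicts outcome but happens to be balanced, which is when adjustment would still gain precision. At stake is power in a trial of 75.

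**Worker.** If a worker-side failure affects several control subjects, their outcomes are not independent. Intervention doses are confirmed by sensor without concurrent DOT, so this particular cause acts on the control arm. That arm has only 25 subjects and carries most of the variance of the comparison. At stake is whether the primary p-value and interval can be taken at face value beyond the particular workers involved.

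**Working it through.** **Inputs from section 9.4:** difference 5 points, SD 6, 50 v 25 subjects, two-sided alpha 0.05. **Assumed, because the protocol gives no figures:** size of the county effect, county split, number of DOT workers, and ICC within worker.

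**1. The plan's own figure.** SE of the difference = 6 × √(1/25 + 1/50) = 1.470. A two-sample t-test on 73 df with noncentrality 5/1.470 has power 91.9%. The stated 92% reproduces. Controls carry (1/25)/(1/25 + 1/50) = two thirds of the variance of the difference.

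**2. County: precision.** Assume the counties differ by 6 points in both arms and one third of subjects are in one county.
- County left out: total variance = 36 + 36 × (1/3)(2/3) = 44; SD = 6.63; SE = 6.63 × √0.06 = 1.625; power about 86%. With a 60/40 split, simulated power is 85%.
- County in the model: residual SD returns to 6. Chance association of county with arm multiplies the variance by about 1 + 1/73, so SE ≈ 1.470 × √1.0137 = 1.480; on 72 df power is about 91%.
- If the county effect is zero, adjusting lowers power by less than one point from 91.9%.

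**3. County: type I error.** Simulated with 40,000 trials per setting, no strata and county left out:
- 6-point effect common to both arms: 5.0%.
- 6-point effect in the DOT arm only: 5.3% with the pooled test, 4.6% with Welch.

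**4. County: chance imbalance.** With one third in one county, SD of the between-arm difference in mix = √(0.33 × 0.67 × (1/50 + 1/25)) = 0.115. A gap of 15 points or more has probability 2 × (1 − Φ(0.15/0.115)), about 19%. With a 6-point county effect, a 15-point gap shifts the contrast by 0.15 × 6 = 0.9 points, against a target of 5.

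**5. Worker correlation in the control arm only.** With m controls per worker, design effect DE = 1 + (m − 1) × ICC. True SE = 6 × √(DE/25 + 1/50). Ratio r = true SE/1.470. True error of the unadjusted 5% test ≈ 2 × (1 − Φ(1.96/r)).

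| Workers (m) | ICC | DE | True SE | r | True error | Simulated |
|---|---|---|---|---|---|---|
| any | 0 | 1.00 | 1.470 | 1.00 | 5.0% | 5.1% |
| 5 (5) | 0.05 | 1.20 | 1.565 | 1.065 | 6.6% | 6.5% |
| 5 (5) | 0.10 | 1.40 | 1.654 | 1.125 | 8.2% | 8.0% |
| 5 (5) | 0.20 | 1.80 | 1.820 | 1.238 | 11.3% | 11.4% |
| 10 (2.5) | 0.10 | 1.15 | 1.541 | 1.049 | 6.2% | – |
| 3 (8.3) | 0.10 | 1.73 | 1.793 | 1.220 | 10.8% | – |

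At 5 workers the SE of the DOT mean rises from 1.20 by 10%, 18% and 34% at ICC 0.05, 0.10 and 0.20.

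**6. Price of modelling workers.** At 5 workers and ICC 0.05, the control-mean variance is 36 × 1.2/25 = 1.728 and the DHFS variance is 36/50 = 0.72. Satterthwaite df = (1.728 + 0.72)²/(1.728²/4 + 0.72²/49) ≈ 7.9. Power falls to about 80%.

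**The case against.** The strongest objection concerns the worker part. Overscheduling and transport failure are events of a day, and they correlate two controls only if both are on the same worker's round at that time. Enrolment runs 27 months (section 3.2). If mean Phase 2 follow-up is 2 to 6 months (assumed), then 25 × 2/27 = 1.9 to 25 × 6/27 = 5.6 controls are on DOT at once. With 5 workers, that is about 0.4 to 1.1 per worker. The calculation above gives each worker a lasting effect on all of that worker's subjects, which no section documents. This stands: it argues for the lower ICCs and against calling the standard error wrong. It does not rule out lasting differences between workers, and without worker identity nobody can look.

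A reader might also infer that the DHFS arm has no shared causes at all. Sections 3.5.1 and 3.5.3 do not support that: the same County and study staff review intervention logs and follow up unconfirmed doses, and one website and one pharmacy serve the arm. What is specific to the control arm is that a missed worker visit itself removes a countable dose.

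On county, section 9.6.1 does let county in if it is imbalanced and prognostic. That limits the harm from imbalance but leaves the choice to the data.

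Finally, section 9.6 says a separate SAP adds detail and takes precedence. Its text is not in the document reviewed, so the point applies to the analysis as the protocol describes it.

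**Conclusion.** The point holds in two parts of different strength.

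**County: firm, modest in size.** The described plan names no stratum and does not commit to a county term. The loss is about 5 power points (86% v 91%) if the county effect is one SD, and nothing if there is no county effect. A reader might infer that missing county strata make the standard error too small. They do not: both counties feed both arms, and simulated type I error stays near 5%. Nor would county strata repair worker correlation.

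**Worker: conditional.** Section 2.2 names the mechanism, and the described analysis cannot detect it. A reader might go further and conclude that the control-arm standard error *is* too small. The documents do not establish that. They give no ICC, no number of workers and no caseload, and the sharing of workers among the 25 controls is inferred. If there are 5 workers with lasting effects, true error is about 6.5% to 11% for ICC 0.05 to 0.20. At ICC 0 nothing changes. This justifies recording the worker and running a sensitivity analysis, but not replacing the primary model, since so few clusters would support the variance estimate.

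**What to change.** 1. **Section 9.6.1 and SAP:** include county (San Diego, Orange) as a fixed covariate in the Phase 2 primary model whatever the observed balance. County is known for every subject, so the cost is one degree of freedom and a sentence.
2. **Section 9.3:** use 2:1 permuted blocks within county for subjects not yet randomised. This is a setting in the central database. Section 10.0 shows that this protocol version postdates November 2014, so some subjects may already be randomised. The covariate in item 1 covers them.
3. **DOT form:** record the worker's ID with each witnessed dose. The nurse already collects these forms (section 6.2.1.5), and the cost analysis already needs outreach-worker visits and hours (section 9.6.2).
4. **SAP:** prespecify, as a sensitivity analysis reported beside the primary model, a worker effect in the control arm only, with small-sample degrees of freedom. Assign each control to the worker who witnessed most of that subject's doses, or use a multiple-membership term.
5. **SAP:** name the GEE cluster unit. Clustering on subject would not address shared workers.

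Downside: with few workers, the interval in item 4 will be wide and the worker variance poorly estimated, which is why it should not be the primary analysis.
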